7.1.2 Formulation, packaging, and labeling

The PrO2™ is a flow-resistive device that provides inspiratory resistance via a fixed 2mm orifice and has Bluetooth connectivity to most IOS/Android devices or Mac/Windows computers. The PrO2™ device and app allows for both 100% adherence monitoring and immediate user biofeedback.

7.1.3 Product use and directions

Participants will be instructed to inspire forcefully through PrO2™ until the device signals that the user has achieved the target resistance (via audible alarm and visible light signal). The research team can implement biofeedback signals at a specific inspiratory resistance, which allows for a precise and individualized training target.

At Visit 1: Participants will download the PrO2™ Fit App from the Apple App Store or Google Play. They will be shown how to set up their own PrO2 Fit account and how to connect with their PrO2™ trainer. Research staff will review the planned dosing to start after visit 2. They will be instructed to try to avoid inferring what treatment assignment they have been given, and to not share any impressions they have developed on treatment assignment. The proper use of the trainer will be taught, including safe storage, cleaning and maintenance. Participants will be taught to create an air-tight seal over the mouthpiece after maximal exhalation. The participant will be instructed to breathe in forcefully until the device alarms then continue to maximal inspiration. At Visit 1, participants will be taught on the device while the alarm is set for 15% of their MIP. They will complete a set of 50 repetitions supervised so their technique is assessed and re-direction can occur if needed.

At Visit 2: participants will have refresher training on the use of the PrO2™ Fit app and will repeat their supervised single set of 50 repetitions while supervised to ensure they have the proper technique and the device is working properly.

Research staff will encourage participant and guardian to discuss a plan to optimize adherence to the IMR intervention. This may include picking particular days of the week (e.g. MWF, TuThS) and particular activities to link with IMR (e.g. in mornings before school, evenings before homework, etc.). Guardians will be asked to commit to helping the participant remember their intervention days.

7.2 Accountability Procedures for the Study Product(s)

The PrO2™ devices will be purchased and provided by PrO2 Health Inc.

8. ASSESSMENT OF SAFETY

8.1 Adverse Event

All adverse events during the study period will be collected.

An **adverse event (AE)** is any untoward medical occurrence in humans, whether or not considered study drug-related, which occurs during the conduct of a clinical trial. Any change in clinical status, ECGs, routine labs, x-rays, physical examinations, etc., that is considered clinically significant by the study investigator is considered an AE.

An **unexpected Adverse Event** is defined as any adverse event, the nature, specificity, or severity of which is not consistent with the applicable product information (e.g., package insert/approved label) or investigational plan.

A **suspected adverse reaction (SAR)** is any adverse event for which there is a reasonable possibility that the study intervention caused the adverse event. A reasonable possibility implies that there is evidence that the study intervention caused the event. An **adverse reaction** is any AE caused by the study intervention.

8.2 Guidelines for Assessing Association of an Adverse Event

A **serious adverse event (SAE)** or **serious suspected adverse reaction** or **serious adverse reaction** as determined by the investigator or the sponsor is an adverse event or suspected adverse reaction that results in any of the following outcomes:

- Death
- Life-threatening AE (“life-threatening” means that the study participant was, in the opinion of the investigator or sponsor, at immediate risk of death from the reaction as it occurred and required immediate intervention)
- Persistent or significant incapacity or substantial disruption of the ability to conduct normal life functions
- Inpatient hospitalization or prolongation of existing hospitalization
- Congenital abnormality or birth defect
- Important medical event that may not result in one of the above outcomes, but may jeopardize the health of the study participant or require medical or surgical intervention to prevent one of the outcomes listed in the above definition of serious event

8.3 Guidelines for Assessing Intensity of an Adverse Event

The investigator/delegate (defined as a clinician licensed to make a diagnosis) should use the following definitions when assessing intensity of an adverse event:

- **Mild** - Participant is aware of symptoms or has minor findings but tolerates them well, and no or minimal intervention required.
- **Moderate** - Participant experiences enough symptoms or findings to require intervention.
- **Severe** - Participant experiences symptoms or findings that require significant intervention.

8.4 Guidelines for Assessing Causality

The investigator/delegate (defined as a clinician licensed to make a diagnosis) will use the following question when assessing causality of an AE to study intervention: Is there a reasonable possibility that the intervention caused the event? “Reasonable possibility” means that there is evidence to suggest a causal relationship between the study

intervention and the AE. An affirmative answer designates the event as a suspected adverse reaction. The investigator/delegate (defined as a clinician licensed to make a diagnosis) must document their assessment of severity and causality in the participant records in a timely manner and submit safety reports as required by their IRB/REB/IEC.

8.5 Collection Period and Reporting Procedures

Adverse event information will be gained from direct monitoring of the study participants as well as from clinician observation and self-reporting by the study participants. The investigator/delegate (defined as a clinician licensed to make a diagnosis) must document their assessment of intensity and causality in the participant records in a timely manner and submit safety reports as required by their IRB.

8.5.1 Adverse Events and Serious Adverse Events

Adverse events (AEs) and SAEs will be reported from the time of consent through the end of study participation.

Participants who have study intervention stopped due to a safety concern will be followed for an additional 7 days from the time the intervention was stopped.

Adverse events (AEs) will be followed until resolution, even if this extends beyond the study-reporting period. Resolution of an AE is defined as the return to pretreatment status or stabilization of the condition with the expectation that it will remain chronic.

Adverse events (AEs) will be entered in the data system within 7 days of identification. Serious adverse events (SAEs) will be entered in the data system within 24 hours of identification.

Any SAE entered in the EDC system will generate an automatic email notification to the DCC, BPCA medical monitor, and the sponsor. The BPCA medical monitor will review all SAEs at the time they are reported. The investigator/delegate (defined as a clinician licensed to make a diagnosis) must document their assessment of severity and causality in the participant records in a timely manner and submit safety reports as required by their Institutional Review Board (IRB)/ Research Ethics Board (REB)/ Institutional Ethics Committee (IEC).

8.5.2 Suspected Unexpected Serious Adverse Reactions (SUSARs)

Serious, unexpected, suspected adverse reactions related to terbutaline sulfate will be reported from the time of first study procedure through the end of study participation. SUSARs can be elicited at any time during the defined study period. SUSARs will be entered in the data system within 24 hours of site awareness.

8.6 Event of Special Interest

Not applicable.

8.7 Safety Interim Analysis

No interim analysis is planned.

9. STUDY HALTING/TERMINATION

9.1 Study or Site Halting/Termination Criteria

This study may be terminated at any time by the study PI or sponsor. Reasons for termination include but are not limited to, if in their judgment, there are no further benefits to be achieved from the study, or, if the treatment presents an unreasonable and significant risk to participants. If the study is terminated, notifications will be made to the regulatory authorities, investigators, or study participants, as appropriate, in accordance with all applicable regulations governing the study and site/investigator.

9.2 Halting Rules

No halting rules are planned.

Individual participant stopping criteria are outlined in the section above titled Study Investigator/Sponsor Decides to Withdraw Participant

10. STATISTICAL CONSIDERATIONS

10.1 Study Hypotheses

Primary Specific Aims: Compare measures of satisfaction, adherence and safety between patients randomized to IMR as compared to sham to demonstrate IMR as an acceptable add-on intervention that promotes greater activity in children with obesity with no safety concerns. More satisfaction and adherence are expected in the IMR group compared to sham.

- Hypothesis 1: More than 80% of participants will be satisfied with active IMR at study completion.
- Hypothesis 2: Total active IMR adherence will be >80% of planned IMR repetitions.
- Hypothesis 3: Active IMR will not be associated with any serious adverse reactions.

Secondary Aim: Compare inspiratory strength (measured by mean change in MIP) in IMR versus sham participants to demonstrate changes in inspiratory muscle functioning and dyspnea following IMR. Also, to demonstrate changes in daily physical activity following IMR versus sham participants.

- Hypothesis 1: IMR will significantly increase inspiratory strength (measured by mean change in MIP) with more improvements in IMR compared to participants receiving sham.
- Hypothesis 2: IMR will reduce patient-reported dyspnea scores from activities of daily living and during the step test.
- Hypothesis 3: IMR will lead to reduced sedentary time, increased moderate-strenuous time and increased total daily activity measured by a wrist-worn continuous activity tracking monitor.

Exploratory Aim: Demonstrate changes in exercise capacity following IMR versus sham participants.

- Hypothesis 1: IMR will reduce the peak heart rate increase induced by the step test in IMR compared to sham participants.

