3. OBJECTIVES AND OUTCOME MEASURES

Table 1 Objectives and Outcomes Measures			
Primary Objectives	Outcome Measures	Endpoints	Analysis
Demonstrate IMR as an acceptable add-on intervention in children with obesity.	1. completion of study Visit 3 (V3) 2. adherence to active IMR 3. participant satisfaction among active IMR participants	1. prevalence of completer status 2. prevalence of IMR completion (actual / planned reps over intervention period) in active IMR group 3. prevalence of agree or strongly agree to question of satisfaction with active IMR	Simple descriptive statistics: calculation of prevalence
Secondary Objectives	Outcome Measures	Endpoints	Analysis
Demonstrate changes in inspiratory muscle functioning and dyspnea reporting following IMR	1. Maximum inspiratory pressure (MIP) 2. Baseline Dyspnea Index score 3. MRC breathlessness scale	1. change in MIP over intervention period 2. change in dyspnea scores over intervention period	Analysis of covariance (ANCOVA)
Demonstrate changes in daily physical activity following IMR	1. moderate-vigorous physical activity (MVPA) time 2. sedentary physical activity (SPA) time 3. total steps	1. change in average daily MVPA time 2. change in average daily SPA time 3. change in average daily step count	Analysis of covariance (ANCOVA)
Exploratory Objectives	Outcome Measures	Endpoints	Analysis
Demonstrate changes in exercise capacity following IMR	1. heart rate during 3 minute step test	1. heart rate change during 3-minute step test	Analysis of covariance (ANCOVA)

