10.10 Efficacy Analyses

Aim 1: We will use exact 95% confidence intervals and Fisher's exact test to report and compare the expected satisfaction, adherence and SAE percentages within the IMR compared to the sham group.

Aim 2: We will use analysis of covariance (ANCOVA) to estimate and test the difference in mean 6-week change between treatment groups (IMR versus Sham) for each outcome adjusting for the baseline value of the outcome variable. Given the small sample size, sex (male/female), age, and BMI will each be evaluated in separate ANCOVA models. We will report adjusted (least squares) means with 95% confidence intervals (CI) for each group, as well as the estimated between-group difference in means with 95% CI and p-value for testing the null hypothesis of no difference between group means. The model assumptions will be verified for each outcome, and model fit will be assessed using residual plots.

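### The Aim 1 comparison of IMR with sham by Fisher's exact test does not address the active-arm acceptability targets, and it does not fit adherence as defined

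*Combined protocol and SAP*

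**What the plan says.** - **Section 10.1 (primary aim):** "Compare measures of satisfaction, adherence and safety between patients randomized to IMR as compared to sham to demonstrate IMR as an acceptable add-on intervention". It adds: "More satisfaction and adherence are expected in the IMR group compared to sham".
- **Section 10.1 (numbered hypotheses):** all three are about active IMR. More than 80% of participants are satisfied, adherence exceeds 80% of planned repetitions, and "Active IMR will not be associated with any serious adverse reactions". Section 2.1 gives the same targets.
- **Section 10.2 (Aim 1):** satisfaction with active IMR among completers, active IMR adherence as a percentage of planned repetitions (with completer status in brackets), and serious adverse events among those who received active IMR.
- **Section 10.10 (Aim 1):** "We will use exact 95% confidence intervals", together with Fisher's exact test, to "report and compare the expected satisfaction, adherence and SAE percentages within the IMR compared to the sham group".
- **Section 3, Table 1 (primary objective):** the analysis is "Simple descriptive statistics: calculation of prevalence". The endpoints are "prevalence of completer status", "prevalence of IMR completion (actual / planned reps over intervention period) in active IMR group", and the proportion satisfied with active IMR. There is no safety endpoint.
- **Section 4.10:** study completion means being enrolled and completing Visit 3.

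**The concern.** There are two faults and one minor inconsistency.

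1. Acceptability is framed as something shown by comparison with sham, while every stated criterion is a level to be reached, or an event to be absent, in the active arm. The test and the criterion can disagree in either direction. Section 10.7 sets two-sided p<0.05 as the general standard of significance. A non-significant Fisher result could therefore be reported against a target that was met, and a significant one in favour of a target that was missed. For safety, a non-significant result could be read as reassurance that it does not give.

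2. Fisher's test and the exact binomial interval need one yes/no value per child. Adherence as defined is a ratio of repetitions. A cut-off would have to be supplied later, and a primary-aim result would then depend on that choice.

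3. The Aim 1 endpoint lists in Table 1 and Section 10.2 do not match.

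**Working it through.** **The plan's own figures.** Table 5 is the only power statement. Its method is a two-sided two-sample t-test at alpha 0.05, with noncentrality d × √(n/2) and N−2 degrees of freedom. This gives 0.509 for d=0.75, N=30 and 0.833 for d=1.25, N=24, as printed. All 24 cells agree to within 0.0005. The table concerns differences in means, so it says nothing about Aim 1.

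**Inputs.** 15 children per arm (Section 4.1); two-sided 0.05 (Section 10.7); targets above 80% (Section 10.1). The counts below are illustrations.

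**Satisfaction: test against target.**
- 13/15 versus 13/15: active arm 13/15 = 86.7%, target met. The observed table is the most probable one given its margins, so p=1.00.
- 9/15 versus 2/15: active arm 60%, target missed. With 11 satisfied in total, P(9 in active) = C(15,9) × C(15,2) / C(30,11) = 525,525 / 54,627,300 = 0.00962. Adding P(10)=0.00082 and P(11)=0.00002 gives 0.01047. Doubling, because the arms are equal, gives p=0.021.
- With 13/15 in the active arm, 7/15 on sham gives p=0.0502 and 6/15 gives p=0.021. Significance therefore needs sham satisfaction of 40% or lower.

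**Serious adverse events.**
- 4/15 versus 0/15: 2 × C(15,4) / C(30,4) = 2 × 1,365 / 27,405 = 0.0996.
- 5/15 versus 0/15: 2 × C(15,5) / C(30,5) = 2 × 3,003 / 142,506 = 0.042.

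Four events against none would still be non-significant.

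**What active-arm estimation can deliver at n=15 (Clopper-Pearson 95%).**
- 13/15: 59.5% to 98.3%. 14/15: 68.1% to 99.8%.
- 15/15: lower limit 0.025^(1/15) = 78.2%. No result excludes 80%. With 12 completers, 12/12 has a lower limit of 73.5%.
- An observed rate above 80% means at least 13/15. If the true rate is exactly 80%, this has probability 0.231 + 0.132 + 0.035 = 0.398.
- 0/15 serious reactions: upper limit 1 − 0.025^(1/15) = 21.8%.

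**Adherence.** Table 1 and Section 10.2 both define it as repetitions done over repetitions planned, which gives each child a value on a continuous scale. The bracketed completer status in Section 10.2 does not turn this into a yes/no variable, because Section 4.10 ties completion to Visit 3 and not to repetitions. A mean across 15 children has a 95% half-width of t(14) × SD / √15 = 2.145 × SD / 3.873. That is 8.3, 11.1 or 16.6 percentage points for an SD of 15, 20 or 30. The documents give no SD, so these are assumed values.

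**Endpoint lists side by side.**

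| Item | Table 1 | Section 10.2 |
|---|---|---|
| Visit 3 completion | yes | no separate item |
| Satisfaction, active IMR | yes | yes |
| Adherence, active IMR | yes | yes, labelled completer status |
| Safety | no | serious adverse events |

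Hypothesis 3 is about serious adverse reactions. Sections 8.1 and 8.2 distinguish reactions from events.

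**The case against.** The strongest reply is that the plan already contains the right analysis. The 80% criteria stand directly below the comparison sentence in Section 10.1, Section 10.10 plans exact confidence intervals, and Table 1 plans prevalence only. Section 10.7 already summarises continuous outcomes by arm with mean, SD and quartiles. Section 10.6 calls the study exploratory and Section 10.11 treats it as a pilot. All of this stands.

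A reader might infer that the Fisher p-value decides whether IMR is acceptable. The documents do not say so; they leave its role unstated beside a sentence about demonstrating acceptability. A reader might also infer that repetitions will be pooled across children as independent trials. Nothing in the plan proposes that. The example of 9/15 versus 2/15 requires very low satisfaction on sham, so it shows that test and target can part company, not that this is likely.

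Section 10.4 requires the analysis plan to be approved before the final analysis, which runs on blinded data. This gives some protection against a chosen cut-off, but only some: under Section 4.3 staff review each child's adherence weekly, so adherence is known well before unblinding.

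The endpoint-list differences are mostly editorial. Disposition, drop-out and adverse events are summarised anyway (Sections 10.7 and 10.8), and causality is assessed (Section 8.4).

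What remains is that a between-arm test is offered in support of active-arm targets it does not measure, and that it is applied to a variable it does not fit.

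**Conclusion.** The point holds in this limited form. As written, Sections 10.1 and 10.10 attach to the primary aim a comparison that does not address its hypotheses, and Section 10.10 names methods for adherence that cannot be used without a missing definition. The counts show the mismatch: p=1.00 with the target met, p=0.021 with it missed, and 5 versus 0 serious adverse events needed for significance. These figures assume 15 evaluable children per arm; fewer completers make the intervals wider.

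The documents do not support the stronger reading that Aim 1 lacks an active-arm analysis or that success depends on the Fisher test. The correction should be made because the primary aim is affected and the cost is low. It does not threaten the trial's validity.

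**What to change.** 1. **Role of the comparison (10.1, 10.10).** State that Aim 1 is judged by active-arm estimates with 95% confidence intervals against the 80% targets. Show sham descriptively and call any Fisher p-value supportive. Remove the expectation of doing better than sham as evidence of acceptability. State that at 15 per arm 80% is a point-estimate target only: no result puts the exact lower limit above it, and an observed rate above 80% occurs about 40% of the time when the true rate is 80%.
2. **Adherence (10.10).** Replace Fisher's test and the exact binomial interval with each child's percentage of planned repetitions, reporting the mean and 95% confidence interval across children beside the Section 10.7 summaries. If a yes/no version is kept, fix its cut-off before any adherence data are reviewed, or label it post hoc.
3. **Minor alignment.** Use one Aim 1 list in Table 1, 10.2 and 10.10: Visit 3 completion, satisfaction, adherence and safety. Under safety, report serious adverse reactions to match Hypothesis 3 as well as all serious adverse events.

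Cost: no added patients, visits or data. It is an amendment to the analysis plan, since it changes the stated role of a primary-aim test. The Aim 1 p-values become supportive and the claims more modest.

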10.2 Objectives and Endpoints

Aim 1:

- Satisfaction with active IMR (yes/no) as an intervention rated at study completion measured as a percentage of study completers.
- Active IMR adherence measured as a percentage of planned IMR repetitions (completer status).
- Serious adverse events (yes/no) measured as a percentage of participants receiving at least one active IMR intervention.

Aim 2:

- Change in maximum inspiratory pressure as measured by maximal inspiration in centimeters of water.
- Change in dyspnea as measured retrospectively of activities of daily living.
- Change in sedentary time measured by mean daily sedentary time assessed by the Vivosmart 4 activity tracker.

- Change in moderate-strenuous physical activity time measured by the mean daily MVPA time assessed by the Vivosmart 4 activity tracker.
- Change in total daily activity measured by mean daily step count and mean daily calorie expenditure.

Aim 3:

- Change in heart rate during step test.

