Together, we propose **BREATHE Fit**, a randomized SHAM-controlled 6-week trial of inspiratory muscle rehabilitation in children aged 8-17 years with obesity enrolled in the Duke HL. **Primary research question:** *Is IMR an acceptable add-on intervention that promotes greater activity in children with obesity?* The **BREATHE Fit** trial will address the following aims:

Aim 1. Demonstrate the acceptability of IMR in children with obesity.

Hypothesis 1a (H1a). More than 80% of participants will be satisfied with active IMR at study completion. H1b. Total IMR adherence will be >80% of planned active IMR repetitions. H1c. Active IMR will not be associated with any serious adverse reactions.

Aim 2. Demonstrate changes in inspiratory muscle functioning and dyspnea reporting following IMR. H2a. IMR will significantly increase inspiratory strength (measured by mean change in MIP). H2b. IMR will reduce patient-reported retrospective dyspnea scores during activities of daily living.

Aim 3. Demonstrate changes in daily physical activity following IMR.

H3a. IMR will lead to reduced sedentary time, increased moderate-strenuous time and increased total daily activity measured by a wrist-worn continuous activity tracking monitor.

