2.4.3 Risks of stair-step challenge

The stair-step challenge is a generally safe exercise procedure conducted in the outpatient setting. There is a small chance of tripping or falling during the procedure and possible resulting injury. Close supervision and spotting of the participant will take place to reduce the chance of injury.

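### Does counting all-cause SAEs leave the hypothesis of no serious adverse reactions (H1c) untested?

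*Combined protocol and SAP*

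**What the plan says.** The safety hypothesis appears twice in the same words, as H1c in Section 2.1 and as Hypothesis 3 of the primary aims in Section 10.1: "Active IMR will not be associated with any serious adverse reactions". The aim above it in Section 10.1 is to compare safety between IMR and sham.

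The Aim 1 endpoint in Section 10.2 is "Serious adverse events (yes/no) measured as a percentage of participants receiving at least one active IMR intervention". Section 10.10 then plans to "report and compare the expected satisfaction, adherence and SAE percentages within the IMR compared to the sham group"; the tools named are Fisher's test and exact 95% intervals.

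Section 8 keeps the terms apart. An adverse event counts whether or not it is related to the intervention, while an adverse reaction "is any AE caused by the study intervention" (Section 8.1). Seriousness, "as determined by the investigator or the sponsor is an adverse event or suspected adverse reaction that results in any of the following outcomes" (Section 8.2), applies to both. For each event a clinician judges whether there is a reasonable possibility of causation: "An affirmative answer designates the event as a suspected adverse reaction" (Section 8.4). Section 8.5.1 sets the reporting period for AEs and SAEs from consent to the end of participation, with 7 further days of follow-up after a safety stop.

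**The concern.** By the protocol's own definitions, the endpoint counts more than the hypothesis speaks of. A serious event unconnected with the trainer enters the endpoint but does not contradict the hypothesis. Such events can be foreseen: Section 2.4.3 says of the step test that "There is a small chance of tripping or falling during the procedure and possible resulting injury", and the test is done at Visits 2 and 3.

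Two related points add to the impression of a gap. Section 10.2 does not say whether an SAE between consent and the first assigned session counts, although reporting opens at consent, which is 10 to 14 days before randomisation by preference and extendable to 28 (Table 4, note a). The denominator in Section 10.2 also mentions only active IMR, whereas Section 10.10 compares with sham.

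At stake would be the reading of a primary-aim safety result: a non-zero percentage might be taken as evidence against H1c when no serious reaction had occurred, or the choice of count might be made after the events were known.

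**Working it through.** The documents give no figure for the safety endpoint, so there is none to reproduce. Table 5 concerns differences in means and is unaffected.

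**Inputs.** 15 participants per arm (Section 4.1); exact 95% intervals and Fisher's exact test (Section 10.10); two-sided 5% level (Section 10.7).

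**1. Size of the possible discrepancy.** Suppose one unrelated SAE and no serious reaction in the active arm.

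- All-cause count: 1/15 = 6.7%. Exact lower limit 1 − 0.975^(1/15) = 0.0017. The upper limit solves (1 − p)^15 + 15p(1 − p)^14 = 0.025, giving p = 0.3195. The interval is 0.2% to 31.9%.
- Reaction count: 0/15 = 0%. Upper limit 1 − 0.025^(1/15) = 0.218, so 0% to 21.8%.

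The two intervals overlap almost entirely.

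**2. How often this could arise.** The documents give no background SAE rate. If the risk r of an unrelated SAE per participant is assumed to be 1%, 2% or 5%, the chance of at least one among 15 is 1 − (1 − r)^15:

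| Assumed r | Chance of at least one |
|---|---|
| 1% | 14% |
| 2% | 26% |
| 5% | 54% |

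Nothing in the documents favours one of these rates. They show only how the chance grows with r.

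**3. Direction of the error.** Serious reactions are a subset of SAEs, so the number of participants with a reaction cannot exceed the number with an SAE. Zero SAEs implies zero serious reactions. Any discrepancy counts against IMR.

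**4. What the comparison with sham can show.** With no sham events and k active events, the two-sided Fisher p-value is 2 × C(15,k)/C(30,k):

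- k = 1: 2 × 15/30 = 1.0
- k = 4: 2 × 1,365/27,405 = 0.100
- k = 5: 2 × 3,003/142,506 = 0.042

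One stray event gives no signal of harm. Equally, the test has little power at low counts, whether all SAEs or only related ones are counted.

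**5. Events before training.** The denominator requires at least one session. Section 6.2.2 re-confirms eligibility before randomisation and bars anyone who newly meets an exclusion criterion; Section 5.2 excludes recent musculoskeletal injury or illness and any condition that the investigator considers unsafe. Many children with a serious event after consent would therefore never enter the denominator. The route is narrow, though not closed.

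**6. Denominator.** Section 10.3 defines the analysis population as those randomised with at least one IMR intervention, and Section 10.7 summarises adverse events by intervention group. Read with Section 10.10, these give a denominator for each arm.

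**The case for a change.** The best argument for a change is that safety is among the primary aims, the mismatch is plain on the page, and nothing in Section 10 says that the recorded causality judgement will be used. Since Fisher's test needs five events against none to reach significance, it cannot separate related from unrelated events at realistic counts; only the causality judgement can. A sentence naming the related count as the H1c result would cost nothing and would remove any choice made after events are seen.

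The textual point stands, and so does the point about Fisher's test. The need for a change does not follow.

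- The hypothesis is that IMR is not associated with serious reactions, and the aim is a comparison with sham. An all-cause count by randomised arm addresses association without case-by-case attribution. That is a real advantage where Sections 4.2 and 5.4.1 accept that participants may guess their assignment.
- Attribution is not clear-cut. A fall in the step test is not automatically unrelated, because Section 2.4.1 lists dizziness and dyspnea among the possible effects of IMR.
- Using suspected reactions would not match the hypothesis exactly either, since Section 8.1 separates a suspected reaction from one that is caused. Which count should lead is partly preference.
- A reporting period does exist, in Section 8.5.1. What is unstated is only whether the endpoint counts from consent or from the first session.

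A separate inconsistency touches that start point: Section 7.1.3 describes a supervised practice set at Visit 1, while Table 4 places device training and MIP measurement only at Visit 2. Those passages must be reconciled in their own right. The practice set precedes randomisation, so it does not distinguish the arms.

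**Conclusion.** The wording of hypothesis and endpoint differs, but the plan as written still supports a sound safety conclusion, and no change is called for. The planned measure is the broader one and errs only towards overstating harm. The discrepancy from a single unrelated event is 6.7% against 0%, with wide and overlapping exact intervals. The related count needs no new data, because seriousness and causality are documented for each event. No pass/fail threshold depends on the percentage, and Section 9.2 plans no halting rules. With at most a handful of SAEs expected among 15 children, an analyst would report each one with its timing and causality beside the by-arm percentage. Section 10.4, which requires the analysis plan to be finalised and approved before the final analysis, gives a natural place to write that down.

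This conclusion rests on two assumptions: that causality is recorded as Sections 8.4 and 8.5.1 require, and that SAEs are few enough to describe individually. The size of the discrepancy assumes 15 treated participants in the active arm; the chance of its arising depends on a background rate that the documents do not give.
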